### **2.3.1. Benefits**

The current study (Study INS1007-211) is not designed to demonstrate clinical benefit for participants. However, the results of this study are necessary for determining the clinical benefit to and the correct dosing of brensocatic in patients with CF. This study will be undertaken in support of the development of a safe and efficacious treatment for CF.

The characteristics of brensocatic that make it a promising candidate for treatment of CF are the following, as observed in the Phase 2 study of participants with NCFBE:

- Both doses of brensocatic (10 and 25 mg QD for 24 weeks) in Study INS1007-201 provided statistically significant and clinically relevant prolongation of time to PE compared with placebo
- In Study INS1007-201, brensocatic 10 mg QD for 24 weeks provided a statistically significant and clinically relevant treatment effect on the annualized rate of PEs compared with placebo, and brensocatic 25 mg QD for 24 weeks showed a numerically lower rate of PEs than with placebo
- Brensocatic reduced sputum NE concentrations in a dose-dependent manner, supporting the proposed mechanism of action
- Achievement of sputum NE concentrations below the limit of quantification postbaseline provided a clinically relevant and statistically significant effect on time to PE

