3.3. Exploratory Objectives and Estimands

Pharmacodynamic Objective(s)	
To evaluate the effect of brensocatib compared with placebo on the concentration of Neutrophil Elastase (NE), Cathepsin G (CatG), and Proteinase 3 (PR3) in sputum over the 28-day treatment period	
Population	Participants with CF defined by the inclusion and exclusion criteria of the CSP
Treatment Regimen	1 tablet QD of brensocatib or placebo (actual treatment)
Endpoints	Percentage inhibition from baseline to Day 14 and Day 28 for concentration of NE, CatG, and PR3 in sputum
Population Level Summary	Treatment means for observed values and for percent inhibition from baseline
ICE	
 • Early discontinuation from randomized IP for any reason, • Use of antibiotics during an acute event that could affect neutrophil serine protease (NSP) levels
Strategy	The While-On-Treatment strategy (including up to Day 35 follow-up period) will be applied for both ICEs.

Pharmacodynamic Objective(s)	
To evaluate the effect of brensocatib compared with placebo on the concentration of NE, CatG, and PR3 in blood over the 28-day treatment period	
Population	Participants with CF defined by the inclusion and exclusion criteria of the CSP

Treatment Regimen	1 tablet QD of brensocatib or placebo (actual treatment)
Endpoints	Percentage inhibition from baseline to Day 14 and Day 28 for concentration of NE, CatG, and PR3 in blood
Population Level Summary	Treatment means for observed values and for percent inhibition from baseline
ICE	
 • Early discontinuation from randomized IP for any reason, • Use of antibiotics during an acute event that could affect NSP levels
Strategy	The While-On-Treatment strategy (including up to Day 35 follow-up period) will be applied for both ICEs.

Efficacy Objective(s)	
To assess the effect of brensocatib compared with placebo on lung function, as measured by change in pulmonary function tests including ppFEV ₁ , FEV ₁ , FVC, and FEF _(25-75%) at Day 28	
Population	Participants with CF defined by the inclusion and exclusion criteria of the CSP
Treatment Regimen	1 tablet QD of brensocatib or placebo (randomized treatment)
Endpoints	Change from Baseline to Day 28 in prebronchodilator ppFEV ₁ , FEV ₁ , FVC, and FEF _(25-75%)
Population Level Summary	Treatment means or difference in means if data allow estimation based on a statistical model

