7. GENERAL STATISTICAL CONSIDERATIONS

7.1. General

Tables and figures will be provided by treatment group/dose level (10 mg, 25 mg, 40 mg, and 65 mg [if conducted] QD brensocatic, pooled placebo except for PK output). If sample sizes permit, summaries will be further stratified by CFTR modulator and non-modulator.

Treatment arm/dose levels will be presented in this stratified analysis if the number of observations is ≥ 2 . If the assignment to a stratum differs between the randomization file and the eCRF, the randomization file will prevail. In the listings, CFTR modulator use will be indicated by + for participants on CFTR modulator and by - for the non-modulator stratum following the Subject Identifier. For tables in the demographic and safety sections, also a Total column will be presented.

Descriptive statistics for continuous variables will be calculated at scheduled visits (nominal timepoints for PK) and will include the number of participants in the treatment group/dose level of the respective analysis set (N in column header of the table), the number of non-missing- observations (n), the number of observations below limit of quantification (BLQ) for PK and PD tests, arithmetic mean, standard deviation (SD), median, minimum, and maximum. For brensocatic plasma concentrations, the GM with 95% CI and gCV%, for PK parameters (except for t_{\max} and t_{last}), and PD tests, the GM and gCV% will be reported in addition. The GM will be derived by calculating the arithmetic mean of the natural log-transformed observations and then back-transforming the mean by exponentiation. The gCV% will be calculated as: $100 \times \sqrt{\exp[\text{variance of the log-transformed values}] - 1}$. GM and gCV% will only be calculated for quantifiable values above 0. For t_{\max} and t_{last} , only n, median, minimum, and maximum will be presented. For PK parameters, no descriptive statistics will be calculated when fewer than three individual PK parameter values are available. Summaries of continuous variables other than plasma concentrations that have some values recorded using approximate values (e.g., $<$ or $>$) will use the numeric part of the value in calculations. Rules for plasma concentrations BLQ or missing are given in [Section 11](#).

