Categorical variables will be summarized by counts and by percentage of participants in the corresponding categories. The number of participants in the treatment group/dose level of the respective analysis set (N in column header of the table) and the number and percentage of non-missing observations in each category will be provided. A category including missing assessments may be added if appropriate. Footnotes will specify the base for the percentages.

Data from unscheduled visits will not be used in summaries, except for the derivation of baseline.

Listings corresponding to all summaries will be provided. Listings will also show data from unscheduled visits. Listings will be presented by treatment group/dose level, Subject Identifier, and date or visit. Listings will present the data as collected in the eCRF along with variables derived from the eCRF data.

The baseline value for safety data will be the most recent non-missing value prior to the first dose of IP.

The baseline value for efficacy data will be the most recent non-missing value prior to randomization. Note that for PFT, the most recent best effort prior to randomization will be selected.

Change from baseline at visit (i) = observed value at visit (i) – baseline value.

Percent change from baseline at visit (i) =

$$100 * [(observed\ value\ at\ visit\ (i) - baseline\ value) / baseline\ value].$$

Percent inhibition from baseline at visit (i) = $100 * [1 - \text{fold change from baseline at visit (i)}]$,
where fold change from baseline at visit (i) = observed value at visit (i) / baseline value.

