12. PHARMACODYNAMICS

For the general layout of the tables see [Section 7.1](#).

PD Tests NE, CatG, and PR3 will be assessed in blood and in sputum. Baseline is defined in [Section 7.1](#). The most recent non-missing value before the first dose of IP will be used as baseline which is either the assessment at Day 1 pre-dose or if this is not available the assessment at Screening. If both assessments are not available, the participant will not be included in the PD analysis set.

The strategies for the ICEs as outlined in [Section 3.3](#) and [Section 7.2](#) will be applied.

Descriptive statistics (including GM and gCV% for observed values and number of values BLQ) will be provided for observed values and %inhibition from baseline by scheduled visit (on natural scale). %Inhibition from baseline will be calculated as $100 * (1 - \text{fold change from baseline})$, where $\text{fold change} = \text{post baseline value} / \text{baseline value}$. Observed values that are BLQ will be set to 0 in the calculation of descriptive statistics. If sample protein concentration data are available, the activity of NE, CatG and PR3 should be normalized by the protein concentration, to generate activity values of ng/ml/mg protein, and the normalized NSP data will be presented in the same way as described above.

The neutrophil count summary will be included in the safety (hematology) analyses.

The following figures will be provided for each PD test for concentrations in blood and in sputum:

- Mean (+/- SD) over time using scheduled sampling time on natural scale by dose level overlaid in the same figure.
- Mean %inhibition (+/- SD) values over time using scheduled sampling time by dose level overlaid in the same figure.
- Individual participant profiles for PD data over time at scheduled visits – the participant's dose levels will be distinguished by different colors (spaghetti plots).

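### For the exploratory PD markers, values below quantification count as 0 in the mean, drop out of the geometric mean in the same table, and have no rule when they occur at baseline

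*SAP*

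**What the plan says.** SAP Section 12 plans descriptive summaries of the PD markers by scheduled visit: "Descriptive statistics (including GM and gCV% for observed values and number of values BLQ"), together with percent inhibition from baseline. It adds: "Observed values that are BLQ will be set to 0 in the calculation of descriptive statistics".

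SAP Section 7.1 says that PD tests get a GM and gCV% on top of the usual statistics, and restricts both: "GM and gCV% will only be calculated for quantifiable values above 0". It also has a general rule that summaries of variables recorded with a < or > sign "will use the numeric part of the value in calculations". Only plasma concentrations are exempt from that rule.

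Percent inhibition is 100 x (1 - fold change), "where fold change from baseline at visit (i) = observed value at visit (i) / baseline value". Baseline is the last non-missing value before dosing, from Day 1 or else Screening. The one provision for an unusable baseline is: "If both assessments are not available, the participant will not be included in the PD analysis set". A baseline that exists but is BLQ is not mentioned.

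The PD estimands in SAP Section 3.3 are summarised as "Treatment means for observed values and for percent inhibition from baseline".

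Protocol Section 2.3.1 reports from the NCFBE trial: "Achievement of sputum NE concentrations below the limit of quantification postbaseline provided a clinically relevant and statistically significant effect on time to PE". Protocol Section 4.3 links sputum NE below quantification to fewer exacerbations and describes a dose-dependent effect.

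**The concern.** In most assays a BLQ result is a nuisance. Here, for sputum NE, it is the response that the protocol hopes to see, and more of it is expected at higher doses. The handling rule therefore acts on the result itself, and it does so in three ways.

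- **GM of observed values.** Participants who reach BLQ leave the calculation, so the GM describes only those who did not. The stronger the response, the more selected the remainder.
- **Mean percent inhibition.** A post-dose BLQ value over a quantifiable baseline counts as exactly 100%. The true value is somewhat less, so this statistic leans toward a larger effect.
- **BLQ baseline.** Set to 0, it becomes the denominator of the fold change. The endpoint value is then 0/0 or minus infinity, and the arm mean cannot be computed without a decision that the SAP does not contain.

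At stake is whether the PD tables give a coherent picture across doses, and whether the treatment of undefined values is settled before anyone sees the data by arm.

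**Working it through.** The plan states no PD figure to reproduce. The inputs from the documents are the rules above and about 7 participants per active dose (SAP Section 4.1). The PD LLOQ, variability and BLQ share are not given, so every value for them below is an assumption.

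**1. The rules applied to an illustrative arm of 7** (assumed: every baseline 10, LLOQ 1).

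| Post-dose values | Mean, BLQ = 0 | GM, BLQ dropped | Mean inhibition, BLQ = 0 | Mean inhibition, BLQ = LLOQ |
|---|---|---|---|---|
| 8, 7, 6, 5, 4, 3, 2 | 5.00 | 4.55 (n = 7) | 50.0% | 50.0% |
| 8, 7, 6, four BLQ | 21/7 = 3.00 | (8 x 7 x 6)^(1/3) = 6.95 (n = 3) | 70.0% | 64.3% |
| 9, six BLQ | 9/7 = 1.29 | 9.00 (n = 1) | 87.1% | 78.6% |

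Down the table the response strengthens. The mean falls from 5.00 to 1.29 while the GM rises from 4.55 to 9.00, so the two rank the arms in opposite order. The true mean inhibition lies between the last two columns, so BLQ = 0 overstates it by at most 5.7 points in the second arm (70.0 - 64.3) and 8.5 in the third (87.1 - 78.6; 8.6 unrounded).

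With BLQ = LLOQ/2 and all 7 kept, the GMs are 4.55, 1.54 and 0.76, the means 5.00, 3.29 and 1.71, and mean inhibition 50.0%, 67.1% and 82.9%. The rankings agree.

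**2. Size of the GM bias.** Assume lognormal values with log-mean mu and log-SD s, in units of LLOQ. The GM of the quantifiable values is exp(mu + s x phi(a)/(1 - Phi(a))), with a = -mu/s. The apparent reduction is 1 minus the post/baseline ratio of these GMs.

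Example with s = 1, baseline 5 x LLOQ and a true 80% fall:
- Baseline: mu = ln 5 = 1.609, phi/(1 - Phi) = 0.1093/0.9462 = 0.1155, GM = exp(1.725) = 5.61.
- Post-dose: mu = ln 1 = 0, phi/(1 - Phi) = 0.3989/0.5 = 0.798, GM = exp(0.798) = 2.22.
- Apparent reduction: 1 - 2.22/5.61 = 60.4%.

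Apparent reduction for a true 80% fall:

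| Baseline / LLOQ | s = 1 | s = 2 |
|---|---|---|
| 5 | 60.4% | 52.5% |
| 20 | 76.5% | 65.3% |
| 50 | 79.4% | 71.6% |
| 100 | 79.9% | 75.0% |

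**3. Chance of a BLQ baseline.** The probability for one participant is Phi(-ln(baseline/LLOQ)/s). At 10 x LLOQ:
- s = 2: Phi(-1.151) = 12.5%, so 1 - 0.875^7 = 61% for at least one in an arm of 7.
- s = 1: Phi(-2.303) = 1.1%, so about 7%.

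With such a baseline set to 0, a post-dose BLQ value gives 0/0 and any quantifiable value gives minus infinity.

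**The case against.** The strongest reply is that the defect is modest and partly visible. The GM is planned for observed values only, and the PD estimand summary uses means. The SAP never reports 1 minus a ratio of GMs, so the second table measures how far the GMs drift and is not a planned output. BLQ counts, medians, ranges, individual profiles and listings are all planned, so a reader can see how many values the GM omits. All of this stands. It makes the GM problem one of a supporting statistic, but visibility does not correct the GM, and it does nothing for a zero denominator in the estimand summary itself.

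The numeric-part rule is a general default beside a specific PD rule, and the documents do not show whether PD results are recorded with a < sign. This too stands; one sentence settles it.

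Three stronger readings are tempting, and the documents do not support them.
- **The rules flatten the planned dose response.** This can hold for the GM. In mean percent inhibition the BLQ = 0 rule pushes the other way.
- **CF dose selection is compromised.** Protocol Section 2.2 rests dose selection on safety, PK and PK-PD relationships. SAP Section 11.1.4 sends the PK-PD work to a separate analysis plan, which may treat BLQ differently.
- **Mean percent inhibition should be replaced.** An arithmetic mean of ratios is sensitive to one large riser, but percent inhibition is the SAP's chosen endpoint, and replacing it is a preference about endpoints.

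The evidence for BLQ as a drug response concerns sputum NE in NCFBE. Nothing in it shows that BLQ will be common for CatG, PR3 or blood, and Protocol Section 4.3 says NE is higher in CF, which makes a BLQ baseline less likely.

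**Conclusion.** The point holds as an inconsistency in how exploratory PD data are handled. Followed literally, the SAP gives a GM biased upward as response strengthens, a mean percent inhibition biased toward a larger effect, and no computable endpoint value for a participant whose baseline is BLQ. The last rests on reading the 0 rule as covering baseline values, which the SAP does not exclude.

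The size cannot be fixed from the documents. Under the lognormal assumption the GM bias is negligible when baseline is far above LLOQ and the log-SD is about 1. It is large toward the low end of a baseline range of about 5 to 20 x LLOQ, especially with a log-SD of 2, where 5 points still remain at 100 x LLOQ.

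A participant who is BLQ both before and after dosing also leaves the GM without being a responder, so the omitted values are not all strong responses. The matter should be settled before database lock but does not threaten the trial's main conclusions: no hypothesis is tested, PD is exploratory, and primary PK and safety are untouched.

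**What to change.** In SAP Section 12:

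- Use one substitution for BLQ PD values, for example LLOQ/2, at baseline and post-baseline, in means, GM, gCV% and percent inhibition, with the same n for all. Apply it to the raw value before protein normalisation, since a normalised value has no single LLOQ.
- State that this overrides the GM exclusion and the numeric-part rule of Section 7.1 for PD.
- Repeat the summaries with BLQ = LLOQ as a sensitivity analysis.
- Show the percentage BLQ beside the planned count, by arm and visit.
- Add geometric mean fold change with a 95% CI as a supplementary summary, and keep percent inhibition as the stated endpoint.

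The cost is SAP wording, table shells and one extra set of summaries. LLOQ/2 is itself an imputation and leaves residual bias when many values are BLQ. With log-SD 2 and baseline 5 x LLOQ, a true 80% fall shows as about 71%, and as 65% in the LLOQ run. The sensitivity run therefore shows how much the choice matters but does not remove the error.

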13. CHANGES TO PROTOCOL-SPECIFIED ANALYSES

Currently, no changes from the protocol-specified analyses are planned.

A Screened Analysis Set was defined in [Section 6.1](#) in addition to the analysis sets defined in the CSP.

APPENDIX A. CFQ-R

The items in the CFQ-R are expressed either “negatively” or “positively”. To align the direction of expression, some of the items must be recoded before the scores for the domains are calculated. The items 6, 10, 13, 15, 17, 18, 23, 28, 30, 32, 34, and 35 will be re-coded by using the formula: recoded score = 5 - original score.

The QoL domains and symptom scores will be derived in the following way:

CFQ-R Domain/ Symptom Score	Formula ¹
	¹ CFQRx: answer to CFQ-R question from eCRF. CFQRx*: recoded question.
Physical Functioning	$100 * ((\text{mean of (CFQR1, CFQR2, CFQR3, CFQR4, CFQR5, CFQR13*, CFQR19, CFQR20)} - 1) / 3)$ if at least 50% of the questions are non-missing
Role Limitations	$100 * ((\text{mean of (CFQR35*, CFQR36, CFQR37, CFQR38)} - 1) / 3)$ if at least 50% of the questions are non-missing
Vitality	$100 * ((\text{mean of (CFQR6*, CFQR9, CFQR10*, CFQR11)} - 1) / 3)$ if at least 50% of the questions are non-missing
Emotional State	$100 * ((\text{mean of (CFQR7, CFQR8, CFQR12, CFQR31, CFQR33)} - 1) / 3)$ if at least 50% of the questions are non-missing
Social Limitations	$100 * ((\text{mean of (CFQR22, CFQR23*, CFQR27, CFQR28*, CFQR29, CFQR30*)} - 1) / 3)$ if at least 50% of the questions are non-missing
Body Image	$100 * ((\text{mean of (CFQR24, CFQR25, CFQR26)} - 1) / 3)$ if at least 2 questions are non-missing
Eating Disturbances	$100 * ((\text{mean of (CFQR14, CFQR21, CFQR50)} - 1) / 3)$ if at least 2 questions are non-missing
Treatment Burden	$100 * ((\text{mean of (CFQR15*, CFQR16, CFQR17*)} - 1) / 3)$ if at least 2 questions are non-missing
Health Perception	$100 * ((\text{mean of (CFQR18*, CFQR32*, CFQR34*)} - 1) / 3)$ if at least 2 questions are non-missing
Weight	$100 * (\text{CFQR39} - 1) / 3$ if CFQR39 is non-missing
Respiratory	$100 * ((\text{mean of (CFQR40, CFQR41, CFQR42, CFQR44, CFQR45, CFQR46)} - 1) / 3)$ if at least 50% of the questions are non-missing
Digestion	$100 * ((\text{mean of (CFQR47, CFQR48, CFQR49)} - 1) / 3)$ if at least 2 questions are non-missing
